#### **9.2.2.1 Other significant adverse events (OAE)**

During the evaluation of the AE data, GEICAM qualified experts will review the list of AEs that were neither reported as SAEs nor AESIs. Based on the expert's judgment, significant AEs of particular clinical importance may, after consultation with the Global Patient Safety Physician of AstraZeneca, be considered OAEs and reported as such.

A similar review of laboratory, vital signs or ECG data will be performed for identification of OAEs. Examples of these are marked haematological and other laboratory abnormalities, and certain events that lead to intervention (other than those already classified as serious), dose reduction or significant additional treatment.

There are currently no identified OAEs for olaparib.

### **9.2.3      *BRCA1/2* Methylation and expression analysis**

**To explore changes in the methylation status of *BRCA1/2* promoter in germline DNA prior and after treatment discontinuation.**

The methylation status of the *BRCA1* and *2* promoters will be measured in germline DNA from blood cells collected at the beginning of the study and after disease progression or at the end of study treatment for other cause, and in paired primary and metastatic lesions. Methylation status will be provided as a continuous (the methylation value will be obtained from the average of the CpG dinucleotides included in the sequence analysed) and also as a binomial variable (status methylated or not methylated).

If methylation status is a continuous variable, to compare the value of methylation between prior and after treatment, the difference of these values will be used and will be used statistical t (student-Fisher) or Wilcoxon test depending if it must be used a parametric or non-parametric test.

If methylation status is a binomial variable, to compare the value of methylation between prior and after treatment it will be used the McNemar test or exact binomial test.

#### **To correlate germline *BRCA1/2* methylation data with efficacy parameters:**

To evaluate the effect of methylation status with time to event variables (e.g. PFS, OS) it will be used a univariate Cox Regresion model.

To evaluate the effect of methylation status with efficacy rate parameters it will be used chi-square test if both of them are quantitative, and will be used an ANOVA analysis if one variable is quantitative and the other one is qualitative.

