m	
Disease assessment for all patients at baseline will include:
 
 • CT or MRI scan of the chest, abdomen and pelvis (CAP). • Bone scans will be mandatory if the patient has bone disease or if there is any suspicious of bone metastases. Any suspicious abnormalities (ie, hotspots) identified on the bone scans at baseline must be confirmed by X-ray, CT scan with bone windows or MRI. Bone lesions identified at baseline will follow the same assessment schedule as for measurable lesions. • Brain CT or MRI scan is mandatory if the patient has CNS metastases or if there is any suspicious of CNS metastases. • CT or MRI scan of any other sites of disease as clinically indicated. • Clinical assessment of superficial disease which will include photographs of all superficial metastatic lesions. 
All lesion measurements must be recorded in the eCRF. Tumour response will be assessed using RECIST v.1.1. every 8 weeks (+/- 1 week).

n	Bone scans (if applicable) will be repeated if indicated when complete response is identified in target disease or when progression in bone is suspected. Responses should be confirmed according to RECIST v.1.1 after at least 28 days.
r	Only to be performed post-study treatment if disease progression has not yet been confirmed and patients have not begun a new therapy, the tumour assessment will be performed every 8 weeks from the last tumour assessment.
s	The patients will be followed for survival until death, loss to follow-up, withdrawal of consent or study termination by GEICAM. After progression or patient is receiving other therapy, the tumour assessment will be performed according to the standard medical practice. The date of death and all treatments received by the patient after progression (according to the standard medical practice) will be collected in the eCRF.
t	At least one paraffin sample from a metastatic lesion must be sent to the sponsor-designated central laboratory to perform methylation testing and other biomarker analysis related to secondary and exploratory objectives. It is strongly recommended that the metastatic sample has been obtained after previous therapy regimen. Surgery blocks or core biopsies would be acceptable, minimal amount of tumour tissue will be specified in the SMM.

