### 3.1 Sample Size

We have set the null hypothesis (H0) that ORR will be 30% (ORR achieved by TN patients treated with gemcitabine plus carboplatini) versus the alternative hypothesis (H1) that ORR will be 54% (ORR showed by TN *BRCA* mutated patients treated with olaparibii). Using an optimal two-stage Simon model and considering an alpha error of 0.05 and a statistical power of 80%, it will be required to include 31 evaluable patients. Twelve evaluable patients will be enrolled in the first

stage, and if at least 4 patients of them have response, additional patients will be recruited to get a total of 31 evaluable patients. Assuming a 10% dropout rate, the total number of patients to be enrolled is 34. Considering, these data the number of responders needed at the end of stage 2 to reject the null hypothesis is at least 14 responders.

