# **9. STATISTICAL METHODS ANNALYSES**

## **9.1 Statistical Methods**

For descriptive analyses, frequencies, percentages and ninety-five percent confidence intervals of interest will be calculated for categorical variables wherever possible. For continuous variables, standard descriptive statistics, such as total number of observations, number of available data, mean, standard deviation, minimum, percentile 25, median, percentile 75 and maximum will be calculated.

For efficacy analyses the 2-sided 95% confidence interval will be presented wherever possible. A bilateral (2-sided) 5% significance level will be used to assess the statistical significance.

Chi-square  $\chi^2$  test or Fisher exact test will be used to explore the relationship between two qualitative variables. Mann-Whitney-Wilcoxon test will be used to compare a quantitative variable in two independent groups.

Logistic regression models will be used to test the association of co-variables with a binary variable (ORR, CBR) and to estimate odds ratios and their 95% confidence intervals.

Kaplan-Meier Method will be used to estimate the survival function, survival median and probabilities of occurrence of event at a certain point of time.

Cox Proportional Hazards Regression Model will be used to estimate the hazard ratio and assess the association between several risk factors, considered simultaneously, and survival time (PFS, RD, OS).

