## 9.2 Statistical analyses

An exploratory and descriptive analysis will be developed for each variable in the study. All continuous variables will be summarized using the following descriptive statistics: n, mean, median, standard deviation, maximum and minimum and confidence interval (CI) will be performed when this information is considered relevant to describe a unique variable. The frequency and percentages of observed levels will be reported for all categorical measures. Ninety-five percent confidence intervals will be provided for estimates of interest wherever possible.

All statistical tests will be performed with a significance level of 5%, unless otherwise specified. For qualitative comparison of independent samples the Chi-squared test (or Fisher's exact test for 2x2 tables) will be used, while for the quantitative samples Mann-Whitney-U will be used. Logistic regression models will be used to test the association of covariables with objective response (yes/no) and clinical benefit (yes/no), and to estimate odds ratios and their 95% confidence intervals. The Kaplan-Meier limit-product method will be used to estimate PFS and OS. The Kaplan-Meier survival curve will be presented graphically. Median PFS and OS with the 95% confidence interval will be reported. Cox regression models will be used to estimate hazard ratios and its 95% confidence interval. The Wald test will be used to establish the prognostic importance of each covariable.

All efficacy analyses will be based on the **Efficacy** population. Additional efficacy analyses will be performed on the ITT population.

All primary and secondary endpoints based on radiological (and photographic where applicable) assessments of tumor burden (PFS, ORR, CBR and RD) will be derived using the local radiologist's/investigator's assessment.

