#### **To correlate *BRCA1/2* expression with efficacy parameters:**

mRNA levels of *BRCA1* and *2* will be assessed in blood and available tumour samples. Expression data will be given as a continuous or as a binomial variable.

To evaluate the effect of *BRCA1/2* expression with time to event variables (PFS, OS) it will be used a univariate Cox Regression model.

To evaluate the effect of *BRCA1/2* expression with efficacy rate parameters it will be used chi-square test if both of them are quantitative, and will be used an ANOVA analysis if one variable is quantitative and the other one are qualitative.

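### For tumour response, the biomarker associations use only yes/no ORR and CBR, although a continuous measure of shrinkage can be derived from data already collected

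*SAP*

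**What the plan says.** Relating methylation and expression to efficacy is a declared secondary objective (Protocol 2.3, SAP 2.2), with outputs planned as tables 4.2 and 4.5 in SAP section 10.

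SAP 9.2.3 gives two routes for each biomarker. PFS and OS are analysed by univariate Cox regression. For tumour response, the methylation paragraph begins "To evaluate the effect of methylation status with efficacy rate parameters" and names a chi-square test or an ANOVA, depending on variable type. The expression paragraph repeats this: "expression with efficacy rate parameters it will be used chi-square test". SAP 9.1 and 9.2 show that the rates meant are ORR and CBR: "Logistic regression models will be used to test the association of covariables with objective response (yes/no) and clinical benefit (yes/no".

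The biomarkers need not be binary. Methylation is supplied both as an average over CpG sites and as methylated or not; expression may be continuous or binary.

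The tumour measurements exist. Inclusion criterion 9 requires a measurable lesion, Protocol 6.1.1 schedules assessment every 8 weeks, and the disease-assessment footnote of Protocol Attachment 1 states "All lesion measurements must be recorded in the eCRF". Nothing in SAP 9.2 or the section 10 table list uses change in tumour size. The separate table shells are not part of the public documents.

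**The concern.** Objective response is largely a cut through the change in the sum of target-lesion diameters. A patient at 29% shrinkage and one at 10% growth count alike as non-responders, and 31% and 90% shrinkage can both count as partial response. In a large trial that loss is tolerable. In one of about 31 patients, where the question is whether a continuous biomarker tracks olaparib activity, it can decide whether a real relation is seen. If the biomarker is also reduced to yes/no, which the plan permits, the loss compounds. At stake is the yield of a secondary objective, not the primary conclusion.

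**Working it through.** **Inputs from the documents.** 31 evaluable patients, ORR 30% under the null and 54% under the alternative (SAP 3.1); association tests at two-sided 5% (SAP 9.1: "A bilateral (2-sided) 5% significance level will be used to assess the statistical significance"). The biomarker population is a subset of enrolled patients (SAP 4.4), so 31 is close to a ceiling.

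**Assumed, because the documents are silent.** A correlation ρ of 0.3 to 0.7 between a continuous biomarker and percent change, both normal, with response defined as percent change cut to give the stated ORR.

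**The plan's own figure.** An exact search for the optimal Simon design (0.30 versus 0.54, alpha 0.05, power 80%) returns 12 then 31 patients and at least 14 responders, with alpha 0.0428 and power 0.807. So n = 31 reproduces. That design stops at 4 or fewer stage 1 responses. The printed rule stops at 3 or fewer (alpha 0.0503, power 0.861). That is a separate matter, used here only for the chance of stopping at 12. No power is stated for any biomarker analysis.

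**Analytic check.** Cutting a normal outcome at proportion p keeps a fraction E = φ(z)²/[p(1−p)] of the information about a correlation, where z is the normal quantile of p.
- p = 0.30: 0.3477²/0.21 = 0.576, so 31 patients count as about 31 × 0.576 = 17.9.
- p = 0.54: 0.3970²/0.2484 = 0.634, so about 31 × 0.634 = 19.7.

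At ρ = 0.5 the correlation with yes/no response falls to 0.5 × √0.576 = 0.379 or 0.5 × √0.634 = 0.398. With power ≈ Φ(√(n−3) × atanh ρ − 1.96) and √28 = 5.292:
- ρ = 0.5: Φ(2.907 − 1.96) = 0.83
- ρ = 0.398: Φ(2.229 − 1.96) = 0.61
- ρ = 0.379: Φ(2.111 − 1.96) = 0.56

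**Simulation** (n = 31, 20,000 runs per setting, power in percent; ranges in the last two columns cover ORR 30% to 54%):

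| ρ | Pearson, % change | Spearman, % change | ANOVA by response | Loss, Spearman to ANOVA (points) |
|---|---|---|---|---|
| 0.3 | 38 | 34–35 | 24–26 | about 9–11 |
| 0.4 | 63 | 57 | 39–43 | 14–18 |
| 0.5 | 84 | 78–79 | 58–64 | 16–21 |
| 0.6 | 96 | 93–94 | 77–82 | 11–16 |
| 0.7 | 99.6 | 99 | 91–95 | 4–8 |

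**Biomarker dichotomised too.** Fisher's exact test on the 2×2 table has power 33–37% at ρ = 0.5 and 20–23% at ρ = 0.4, which is 34 to 48 points below Spearman on percent change.

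**Less favourable conditions, ρ = 0.5.**
- Protocol 1.2.2 cites germline BRCA1 methylation in 21.5% and 47.1% of breast cancer patients, so many values may sit at a floor. With 21.5% above the floor, Spearman power is 49–54% against 37–42% for Mann-Whitney on response. With 47% above it, the gap is about 18–19 points.
- If the trial stops at 12 patients, power is about 40% (Pearson) against 23–26%. Under the printed rule the chance of stopping there is 49% if ORR is 30% and 4% if it is 54%.
- With the worst 20% of patients tied at the bottom rank and no floor, Spearman power is still 76–78%.

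**The case against.** Four objections carry weight.

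**The plan is not confined to binary outcomes.** A reader might infer that every biomarker–efficacy analysis is dichotomised. SAP 9.2.3 itself contradicts that with its Cox models for PFS and OS. If a biomarker were correlated 0.5 with PFS and nothing were censored, both of which are assumptions, Cox power at n = 31 would be 0.75–0.80, about the same as Spearman on shrinkage. This stands and limits the point to tumour response. It does not close the gap, because PFS and OS are different outcomes from shrinkage.

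**The size is assumed.** A reader might take 20 points as a fixed cost, or conclude that most of the chance of detection is lost. Neither is supported. The loss ranges from about 4 to 21 points, and in one typical setting (ρ = 0.5, 45% responders) a continuous biomarker against yes/no response keeps 0.60 of 0.79, about three quarters. The simulation also treats response as an exact cut of shrinkage, whereas protocol response follows full RECIST and needs confirmation after at least 28 days. That simplification favours percent change.

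**The data are not complete.** Lesion measurements are recorded; percent change must be derived. The efficacy population (SAP 4.2) keeps patients with progression, death or unacceptable toxicity before the first assessment, who may have no follow-up sum. Ranking any of them conflicts with the no-imputation rule in SAP 7.1. This stands and shapes the fix.

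**The plan leaves room.** SAP 9.2.3 and 9.2.4.1 allow further biomarker analyses. True, but none is named for tumour size, and an analysis chosen after the data are seen carries less weight.

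**Conclusion.** The point holds for tumour response only. There, the plan relates methylation and expression to yes/no ORR and CBR and leaves unused a continuous measure that costs nothing to collect. With a continuous biomarker, n = 31, ORR 30–54% and an assumed correlation of 0.3–0.7, the cost is roughly 4 to 21 points of power against Spearman on percent change, and more if the biomarker is dichotomised. Absolute power will be lower if fewer patients have evaluable samples, if the trial stops at 12, or if germline methylation sits at a floor.

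A reader might go further and make percent change the main response variable. The documents do not support that: ORR is the declared primary endpoint, and percent change ignores new lesions and non-target progression. This is a worthwhile low-cost addition to a secondary objective, not a flaw in the primary analysis.

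**What to change.** In SAP 9.2.3, and in tables 4.2 and 4.5, add a pre-specified association of each continuous biomarker with best percent change from baseline in the sum of target-lesion diameters, reported as Spearman's rho with a 95% confidence interval. Keep ORR, CBR, PFS and OS as planned. State three rules with it:
- Patients with progression or death before the first post-baseline scan are ranked worst.
- How patients who stop for toxicity before that scan are handled.
- This ranking is an exception to the no-imputation rule in SAP 7.1.

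The same sentences assign chi-square to two quantitative variables, whereas SAP 9.1 gives it for two qualitative ones; correct that in the same edit.

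The cost is one derived variable, a short paragraph and two table changes, with no new visits, scans or samples. The downsides are one more comparison per biomarker at 5%, and a measure blind to new lesions and non-target progression, which is why ORR and CBR stay.

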#### **To correlate *BRCA1/2* methylation between germline and somatic DNA:**

To compare the continuous values of germline and somatic DNA methylation, the difference of these values will be used and it will be used statistical t (student-Fisher) or Wilcoxon test depending if it must be used a parametric or non-parametric test.

#### **To correlate *BRCA1/2* methylation between primary tumour and metastatic lesions:**

If *BRCA1/2* in metastatic lesions is a continuous variable, to compare the value of *BRCA1/2* between primary tumour and metastatic lesions, the difference of these values will be used and it will be used statistical t (student-Fisher) or Wilcoxon test depending if it must be used a parametric or non-parametric test.

#### **To correlate *BRCA1/2* expression with efficacy parameters:**

mRNA levels of *BRCA1* and *2* will be assessed in blood and available tumour samples. Expression data will be given as a continuous or as a binomial variable.

To evaluate the effect of *BRCA1/2* expression with time to event variables (PFS, OS) it will be used a univariate Cox Regression model.

To evaluate the effect of *BRCA1/2* expression with efficacy rate parameters it will be used chi-square test if both of them are quantitative, and will be used an ANOVA analysis if one variable is quantitative and the other one are qualitative.

#### **To correlate *BRCA1/2* expression with *BRCA1/2* promoter methylation status:**

We will compare *BRCA1/2* expression and *BRCA1/2* promoter methylation status when they are binary data using chi-square test.

If methylation status and expression data are given as continuous variables, they will be compared using statistical t (student-Fisher) or Wilcoxon test depending if it must be used a parametric or non-parametric test.

If appropriate, additional analysis on all these biomarkers may be performed.

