### 2.2 Secondary Objectives

- To analyse other efficacy measures.
  - Clinical Benefit Rate (CBR).
  - Duration of Response (DoR).
  - Progression Free Survival (PFS).
  - Overall Survival (OS).
- To analyse olaparib safety.

- To explore changes in the methylation status of *BRCA1/2* promoter in germline DNA prior and after treatment discontinuation for any reason and correlate germline *BRCA1/2* methylation data with efficacy parameters.
- To correlate *BRCA1/2* methylation between germline and somatic DNA and between primary tumour and metastatic lesions.
- To correlate *BRCA1/2* expression with methylation status of *BRCA1/2* promoter and efficacy parameters.

[figure not shown]

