#### **6.1.2 Secondary End-points**

The following secondary end-points will be studied:

- Clinical Benefit Rate (CBR), Duration of Response (DoR), Progression Free Survival (PFS) and Overall Survival (OS).

- Adverse events defined by the NCI-CTCAE (National Cancer Institute Common Terminology Criteria for Adverse Events) version 4.0.
- The methylation status of *BRCA* 1 and 2 promoters will be measured in germline DNA from blood cells at the beginning of the study and after PD, or at the end of study treatment by other reason, and in paired primary and metastatic lesions. It will be analysed: 1) changes of germline methylation pre- and post-treatment; 2) correlation between germline methylation status and efficacy outcome data; 3) correlation between germline and somatic methylation status and 4) correlation between primary and metastatic lesions.

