	3.1.4	Grade 3 or Higher Treatment-Emergent Adverse Events by System Organ Class and Preferred Term
	3.1.5	Grade 3 or Higher Drug-Related Treatment-Emergent Adverse Events by System Organ Class and Preferred Term
	3.1.6	Most common (at least 10% in any treatment arm) Treatment-Emergent Adverse Events by Preferred Term
	3.1.7	Serious Treatment-Emergent Adverse Events by System Organ Class and Preferred Term Safety Population

	3.1.8	Serious Drug-Related Treatment-Emergent Adverse Events by System Organ Class and Preferred Term Safety Population
	3.1.9	Treatment-Emergent Adverse Events by Grade
	3.1.10	Drug-Related Treatment-Emergent Adverse Events by Grade
	3.1.11	Serious Treatment-Emergent Adverse Events by Grade
	3.1.12	Adverse Events from Laboratory according NCI CTC v4.03 by System Organ Class and Preferred Term
3.1.	Deaths	
	3.2.1	All-Cause Mortality Safety Population
4	OTHER ENDPOINTS	
	4.1	Changes of germline methylation pre and post treatment
	4.2	Correlation between germline methylation status and efficacy outcome data
	4.3	Correlation between germline methylation status and somatic methylation status
	4.4	Correlation of methylation between primary and metastatic lesions
	4.5	Correlation between expression data and promoter methylation status of BRCA1/2 and outcome data
5	EXPLORATORY OBJECTIVES (if performed)	
	5.1	Exploratory biomarkers of response or resistance to Olaparib
	5.2	Review potential pharmacogenomics analyses related to drug response or adverse drug reactions
	5.3	Specific mutations or epigenetic biomarkers identified in pre-therapy tumour specimens as potentially linked to treatment response

*The numbers of tables and figures do not have to match exactly with those of the statistical report. The feasibility and interest of performing some of the described tables and figures based on the available number of patients, data and biological samples.*

*Please see Shells Tables, Listings and Figures.*

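### For continuous data, three secondary biomarker objectives that ask for correlation are assigned only t or Wilcoxon tests, which compare levels and do not measure association

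*SAP*

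**What the plan says.** SAP 2.2 sets out to correlate BRCA1/2 "methylation between germline and somatic DNA and between primary tumour and metastatic lesions", and to correlate expression with promoter methylation. SAP 6.1.2 lists "3) correlation between germline and somatic methylation status and 4) correlation between primary and metastatic lesions". It lists these separately from item 1, the change in germline methylation from before to after treatment. The planned outputs in SAP 10 carry the same word: Table 4.3 is "Correlation between germline methylation status and somatic methylation status", Table 4.4 is "Correlation of methylation between primary and metastatic lesions", and Table 4.5 begins "Correlation between expression data and promoter methylation status of".

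SAP 9.2.3 says methylation will be supplied both as a continuous value (the mean over CpG sites) and as a binary status. Its methods for two continuous measures are:

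- Germline and somatic: "To compare the continuous values of germline and somatic DNA methylation, the difference of these values will be used", tested by t or Wilcoxon.
- Primary and metastatic: "between primary tumour and metastatic lesions, the difference of these values will be used", tested by t or Wilcoxon.
- Expression and methylation: "If methylation status and expression data are given as continuous variables, they will be compared using statistical t (student-Fisher) or Wilcoxon test".

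Protocol 8.2.8 gives the same methods.

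**The concern.** A test on a difference asks whether one level is higher than the other. Correlation asks whether patients who are high on one measure tend to be high, or low, on the other. Either can be present without the other. Protocol 1.2.2 cites data in which blood and tumour BRCA1 methylation were correlated and tumour levels were also higher, so the two questions can have separate answers in this very setting.

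The mismatch is plainest for expression and methylation. An mRNA level and a methylation fraction are different quantities, and a test that their levels are equal has no interpretation. For the two tissue comparisons the paired test answers a real question, but not the one in the objective.

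At stake is the reading of Tables 4.3 to 4.5. Followed as written, the continuous analyses would put a p-value for a level shift under a title that promises correlation.

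**Working it through.** **1. Is an association measure named anywhere else?**

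| Place | Methods named | Association of two continuous biomarkers? |
|---|---|---|
| SAP 9.1, 9.2 | chi-square/Fisher, Mann-Whitney, logistic, Kaplan-Meier, Cox | No |
| SAP 9.2.3, the three correlation objectives | t/Wilcoxon; chi-square for binary expression and methylation | No |
| SAP 9.2.3, closing sentence | optional further analysis, no method named | No |
| SAP 9.2.4.1 | unspecified methods for biomarkers against efficacy and outcome | No |
| Protocol 8.2.8 | as SAP 9.2.3 | No |

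**2. What does the planned test respond to?** The documents give no effect size or power for these objectives, so there is no stated figure to reproduce. The following is an illustration. Inputs: two-sided 5% (SAP 9.1) and n = 31 evaluable patients (SAP 3.1). Assumed: normal data, equal SDs, level shift δ in SD units, correlation ρ.

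The paired t test has noncentrality δ√n / √(2(1 − ρ)) on n − 1 degrees of freedom.

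- ρ = 0, δ = 1, n = 31: √31/√2 = 3.94, so rejection is 96.8%. At n = 12 it is 60.8% and at n = 34 it is 97.9%.
- ρ = 0, δ = 0.5, n = 31: noncentrality 1.97, so rejection is 47.8%.
- δ = 0, any ρ: noncentrality 0, so rejection is 5%.

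Simulation (20,000 data sets per setting, n = 31):

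| True state | Paired t rejects | Spearman rejects |
|---|---|---|
| ρ = 0, δ = 1 | 97% | 5% |
| ρ = 0.9, δ = 0 | 5% | 100% |
| ρ = −0.9, δ = 0 | 5% | 100% |

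Wilcoxon follows the paired t (96% at ρ = 0, δ = 1).

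**3. What would a correlation deliver here?** With SE = √((1 + r²/2)/(n − 3)) on the Fisher z scale, an observed Spearman r = 0.5 at n = 31 has SE = √(1.125/28) = 0.200. The 95% CI is tanh(0.549 ± 1.96 × 0.200) = 0.16 to 0.74. At n = 34 it is 0.17 to 0.73. At n = 12, after a stage 1 stop, it is −0.14 to 0.85.

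**4. Effect of selection.** Inclusion criterion 8 requires a methylated BRCA1 and/or BRCA2 promoter in the metastatic sample, with the cut-off at 25% (Protocol 6.3.2). For the gene that qualified the patient, this restricts the range of the metastatic value. Assume a correlation of 0.5 before selection and enrolment of the top fraction q. With z the (1 − q) normal quantile and λ = φ(z)/q, the remaining variance is v = 1 + zλ − λ². The correlation among enrolled patients is 0.5√v / √(0.75 + 0.25v).

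| q enrolled | v | Correlation after selection | Spearman power, n = 34 |
|---|---|---|---|
| no selection | 1 | 0.50 | 82% |
| 60% | 0.42 | 0.35 | 47% |
| 40% | 0.31 | 0.31 | 37% |
| 20% | 0.22 | 0.26 | 27% |

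**The case against.** The best case for the plan is that these are secondary biomarker analyses with small numbers. The SAP allows further analyses, and the table shells, which are not in the documents, may specify a coefficient. SAP 9.2.4.1 calls the biomarker analyses exploratory and mainly descriptive. SAP 8 and 10 make some of them subject to feasibility. This limits the importance of the point but does not remove it. The closing sentence names no method, and SAP 9.2.4.1 concerns biomarkers against outcome. Nor is correlation loose wording for comparison, since SAP 6.1.2 lists change and correlation as separate items.

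A second objection also stands: selection on metastatic methylation weakens the replacement analysis. Power near 80% for a correlation of 0.5 holds only if 0.5 is the correlation within enrolled patients.

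Four stronger readings are tempting but not supported:

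- That no association test is planned at all. Binary expression and methylation have chi-square, and SAP 9.1 gives chi-square or Fisher for any two qualitative variables. However, the germline–somatic and primary–metastatic paragraphs name no binary method of their own. Among enrolled patients, binary status in the metastatic sample will vary little for the qualifying gene.
- That 31 to 34 pairs is a firm maximum. It is so only if the biomarker population is enrolled patients (SAP 4.4). Protocol 3.1 and 5.3 and SAP 3 allow samples from all registered patients to be used.
- That the cut-off in Protocol 6.3.2 leaves the methylation unit ambiguous. The 25% and the β of 0.25 are one threshold in two notations. Different quantities are reason enough against a level test.
- That selection alone guarantees a germline–somatic level difference. Eligibility is on either gene, so this applies only to the gene that qualified the patient.

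**Conclusion.** The point holds for continuous pairs in all three objectives. It is most serious for expression and methylation, where the named test has no meaning. In the two tissue comparisons the test is valid but answers a different question. The 97% against 5%, and 5% against 100%, contrasts rest on assumed effects. The underlying property does not: with equal means the paired t rejects at its nominal 5% whatever the correlation.

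A reader might infer that the trial's main conclusions are at risk. They are not. Objective response rate, the stage 1 decision and safety are unaffected, and the before-and-after germline tests suit their purpose. The change should be made because the plan as written does not address its own stated objectives, and because naming the coefficient now prevents choosing one after seeing the data.

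**What to change.** In SAP 9.2.3:

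- For the three continuous pairings, name Spearman correlation with a 95% confidence interval and the number of pairs, by gene and tissue.
- For germline–somatic and primary–metastatic methylation, keep the paired t or Wilcoxon only as a description of level shift.
- For expression and methylation, remove t/Wilcoxon when both are continuous. Use the rank-sum test already in SAP 9.1 for continuous expression by methylated or unmethylated status, only where both groups are present.
- Clerical: in the two paragraphs relating methylation and expression to efficacy rates, the chi-square clause should refer to qualitative variables, as SAP 9.1 does, not quantitative ones.
- State that enrolled patients are selected on metastatic BRCA1 and/or BRCA2 methylation, so for the qualifying gene correlations with that sample are attenuated and binary status varies little.

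In SAP 4.4, reconcile the enrolled-only biomarker population with the sections that allow samples from all registered patients, and say which applies to analyses not involving outcome.

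The cost is wording. Protocol 8.2.1 and SAP 1 let the SAP modify the protocol's plans, and require an amendment only for major changes to the primary endpoint or its analysis. Protocol 8.2.8 can be aligned at the next amendment. No new patients, samples or assays are needed.
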